3.3. OVERALL STUDY DESIGN

The study is an international, multicenter, 1:1 randomized, double-blind, placebo-controlled, phase II proof-of-concept trial. It will enroll approximately 66 adult patients hospitalized with ARDS that meet the inclusion criteria, randomly assigned at 1:1 ratio to receive either reparixin 1200 mg (treatment group) through a nasogastric tube or matched placebo (control group) TID for 14 days with optional continuation of treatment up to 21 days, if the patient is still intubated on Day 14. The IMP may be administered orally after extubation and between extubation and day 14 should the patient be able to swallow. In such cases the IMP may be administered either intact or crushed and mixed with a vehicle as per speech swallow evaluation. All patients must receive standard and supportive care according to their clinical status and local guidelines during the whole study period. Although the ventilatory strategy in both groups is in the discretion of the PI, physicians are encouraged to comply with the following ventilator strategy: tidal volume of 4-6 ml/Kg of predicted body weight, a plateau pressure < 30 cm H₂O, driving pressure < 15 cm H₂O to maintain arterial pH > 7.2 and FIO₂/PEEP adjusted to keep SpO₂ $\geq 88\%$ or PaO₂ ≥ 55 mmHg.

Sedation, use of neuromuscular blocking agents or nitric oxide and other inhaled vasodilators, prone positioning, and use of ECMO are left to the PI's discretion and are registered daily on the study's electronic case report form.

Each patient will be involved in the study for up to 60 days. This period consists of informed consent acquisition and screening, randomization and baseline assessments, a post-randomization study period of up to 28 days from the first IMP dose or hospital discharge and a follow-up period of up to day-60. Patients will be assessed daily while hospitalized up to extubation from first IMP administration. The end of this study is defined as the end of follow up.

3.3.1. Rationale for Selection of dose, control group and treatment schedule in the study

The dose and dose regimen have been selected according to the rationale reported in [Section 2.6.3](#).

A double-blind, randomized study design including a placebo group is being adopted as the gold standard to minimize systematic bias and increase baseline comparability between treatment groups. Both groups of patients will receive the current standard of care for ARDS.

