4.2. EXCLUSION CRITERIA

1. Moderate-Severe chronic hepatic disease (as verified by a previously known Child-Pugh score ≥ 7). If baseline Child-Pugh score is not known, it should not be calculated while the patient is acutely ill. In that case, the patient is excluded on the basis of: $\text{ALT}/\text{AST} \geq 3 \times \text{ULN}$ and total bilirubin $> 2 \times \text{ULN}$ or $\text{ALT}/\text{AST} \geq 5 \times \text{ULN}$.
2. Severe chronic renal dysfunction: eGFR (2021 CKD-EPI) $< 30 \text{ mL/min}/1.73\text{m}^2$. If baseline (chronic) renal function is not known the patient is only excluded if in need of acute renal replacement therapy (currently on RRT or to be imminently placed on RRT).
3. Participation in another interventional clinical trial.
4. Patients that are clinically determined to have a high likelihood of death within the next 24 hours based on PI's estimation.
5. Currently receiving ECMO or high frequency oscillatory ventilation.
6. Anticipated extubation within 24 hours of screening. (In such cases, re-screening is allowed if the patient is within the enrollment window).
7. Evidence of GI dysmotility as demonstrated by presence of all the following: persistent gastric distention and enteral feeding intolerance and persistent gastric residuals $> 500 \text{ ml}$.
8. Anticipated transfer to a hospital not participating in the trial within 72 hours of screening.
9. Decision to withhold or withdraw life-sustaining treatment (patients may still be eligible however if they

are committed to full support except cardiopulmonary resuscitation if cardiac arrest occurs).

10. History of:
 - a) Documented allergy/hypersensitivity to sulfonamides, ibuprofen and other COX-1 and 2 inhibitors, and to the study product and/or its excipients.
 - b) Lactase deficiency, galactosemia or glucose-galactose malabsorption.
 - c) History of peptic ulcer, GI bleeding or perforation due to previous NSAID therapy.
11. Active bleeding (excluding menses) from an uncontrolled site that cannot be definitively resolved prior to enrollment.
12. Pregnant or lactating women.
13. Women of childbearing potential and fertile men who do not agree to use at least one primary form of contraception during the study and up to 30 days after the last IMP dose.

For patients non able to personally consent to above due to complications of acute illness and/or its treatment assurances for the above must be given by LR and reiterated by the patient when/if he/she is able to do so.

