4.4 Estimands

4.4.1 Primary estimands

The primary estimand #1 is defined by the following attributes:

- Population: Adult patients hospitalized for Acute Respiratory Distress Syndrome, as defined by the inclusion-exclusion criteria of the study.
- Variables: Oxygenation index (OI) at baseline and at day 7.
- Intercurrent events:
 - Death before Day 7, or at Day 7 if OI is not present, as a terminal event which precludes the observation of the variable, will be handled by the composite strategy. Day 7 value is derived using Study Day based on Date (i.e., Day 7= First IMP Intake + 6), since only date of death is collected. The event will be included in the estimand by imputing for OI at day 7, an extreme unfavorable value characterizing the treatment failure. The 90°

Standard/Forms/Template				
Title		Statistical Analysis Plan Template		
Code		Version	Effective Date	Page
PPD		01	29 Aug 2022	28 of 78

percentile of the distribution of the observed values will be used (the value will be rounded to present only one decimal place only for data presentation, not for imputation).

- For patients that at day 7 are extubated and OI is not evaluable, extubation will be handled by the composite strategy as an event which precludes the observation of the variable of interest. The event will be included in the estimand by imputing for OI at day 7 a sufficiently extreme favorable value characterizing the treatment success. The 10° percentile of the distribution of the observed values will be used (the value will be rounded to present only one decimal place, only for data presentation, not for imputation). A patient is extubated at day 7 if the patient results not intubated in the time range [First IMP Intake Date/Time +132h, First IMP Intake Date/Time +155h and 59 min].
- Treatment discontinuation, which may affect interpretation of the variable, will be handled by the treatment policy strategy. The occurrence of the intercurrent event will be irrelevant. All observed values will be used regardless of occurrence of the intercurrent event. Retrieved dropouts will be used for data imputation of all missing data (not due to death and not due to extubation), whichever is the reason of missingness.
- Population-level summary: Change in oxygenation index (OI) from baseline to day 7

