Primary endpoint "Change in oxygenation index (OI) from baseline to day 7 " [study day based on Date/time]	
OI derivation
 
OI is defined as: % mean airway pressure x FIO2/PaO2, derived as 100 x mean airway pressure x FIO2/PaO2. Following the estimand definition:
 
 - If patient dies before Day 7, or at Day 7 (Day 7 date = Day 1 date + 6, since only date of death -no time- is collected) and OI is missing: OI at day 7 = 90th percentile of the distribution of the primary variable at Day 7. - If patient at Day 7 is extubated* and OI is not evaluable (i.e., if the patient results not intubated* in the time range [First IMP Intake Date/Time +132h, First IMP Intake Date/Time +155h and59 min]): OI at day 7 = 10th percentile of the distribution of the primary variable at Day 7. - Otherwise, OI is set to missing. 
*intubation/extubation status at day 7: check intubations in "Extubation Summary" CRF form. Use the multiple entries of extubation/re-intubation: if the last record of intubations/extubation prior day 7 is an extubation and there are no intubations at day 7, it means the subject was extubated on Day 7. Subjects should reach day 7 to be eligible for this imputation.
 
Collection of data on FiO2/PaO2 and mean airway pressure
 
The implementation of the OI is based on 2 daily forms: "Mechanical Ventilation Parameters" for mean airway pressure, and "Lung Function" for the following parameters: PaO2/FIO2, FIO2, PaO2. FIO2/PaO2, used for the computation of OI, may be derived as 1/(PaO2/FIO2) or by using the individual values of PaO2 and FIO2 (when PaO2/FIO2 is missing) as described in the following section "Missing PaO2/FiO2 or mean airway pressure".
 
Missing PaO2/FiO2 or mean airway pressure
 
In case of missing PaO2/FiO2 for a specific visit, derive it based on the individual values of PaO2 and FiO2, if available. If PaO2 is not available set to missing (PaO2 won't be derived). The same applies for mean airway pressure, if not collected on a specific visit, the OI will be missing for that day.
 
Baseline derivation
 
1 - For each assessment performed on or prior treatment start date/time, derive OI as defined below.
 
1.1 Select the last record of mean airway pressure collected in that day (if on the same date of treatment start date, use only records with time <= time of first exposure to IMP)
 
1.2 - Select the "FiO2/PaO2" which is closest (and non missing) to the selected "mean airway pressure" and occurring on the same timeframe (but assessed on or prior treatment start date/time). Same timeframe here means that it should be considered the date/time of mean airway pressure (detected in step 1.1) +/- 12 hours BUT always considering prior to the first IMP intake. If there is any FiO2/PaO2 available in this timeframe, take that FiO2/PaO2 assessment. If there is no FiO2/PaO2 available in this timeframe, select the FiO2/PaO2 collected in the same exact date of the selected mean airway pressure (selected in step 1.1). If there is no such match, the OI baseline will set as missing.

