--	--

Standard/Forms/Template				
Title		Statistical Analysis Plan Template		
Code		Version	Effective Date	Page
PPD		01	29 Aug 2022	61 of 78

Parameter	Calculation
	
2 - Select the OI record closest to the treatment start date.
 
Note: It's expected that the OI will be derived from the assessments performed on the same day of treatment start date (day 1). If OI not available on day 1, then use the OI available from exact previous day (TRTSDT-1). In case neither exists, then the baseline will be missing
 
Note: In case of multiple records, use the value collected under "Randomization/baseline" visit, if available. Otherwise, use the one collected under the latest timepoint prior treatment start date (i.e.: by order: 1 - "Screening", 2 - "Daily assessments through extubation").
 
Post-baseline daily assessments (i.e., assessment after First IMP intake date/time)
 
For each post-baseline assessment, select the value of mean airway pressure based on the study day rules considering date and time. Select the value FiO2/PaO2 based on the study day rules considering date and time. If there is one measurement of mean airway pressure and one measurement of FiO2/PaO2 falling in that specific study day (as defined by the rules considering date/time), select these values to compute the OI at that day. Do the same for each post baseline day. (Example for day 7. Both mean airway pressure and FiO2/PaO2 should be collected in the window [First IMP Intake+132h, First IMP Intake+155h and 59min])
 
For both mean airway pressure and FiO2/PaO2: In case of more assessments at the same day, keep the assessment closer to the midpoint of the time interval. For instance: 2 assessments at day 7 [First IMP Intake Date/Time +132h, First IMP Intake Date/Time +155h and 59 min], the one closer to 144 hours from 1st IMP will be taken.
 
If multiple records exist at the same distance from the midpoint of the time interval, select the first record collected in the eCRF.
 
In case mean airway pressure and/or FiO2/PaO2 is missing at a specific study day, the value of OI for that day is not derived (the 2 records of mean airway pressure and FiO2/PaO2 should be assessed in the same study day, where study day is intended as derived using date/time).

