Incidence of ECMO by day 14 [study day based on Date]	
Transition to ECMO (Y/N) is collected in "Ventilation - Specific Information" CRF Daily assessments through extubation.
 
Incidence of ECMO at Day 14 :
 
event = "Y" if Transition to ECMO = "Y" and date of daily collection (VSIDAT) is performed between date of 1st IMP intake and Day 14 included.
 
otherwise
 
event = "N" if last available day ≥ 12 (allowed time window of 2 day for Day 14 visit)
 
otherwise event is missing if last available day < 12
 
Day 14= Day1 (date 1st IMP intake) + 13

Standard/Forms/Template				
Title		Statistical Analysis Plan Template		
Code		Version	Effective Date	Page
PPD		01	29 Aug 2022	67 of 78

Parameter	Calculation
Use of Vasoactive Medication by day 14 [study day based on Date/time]	
Use of Vasoactive Medications is collected in "Ventilation - Specific Information" CRF Daily assessments through extubation.
 
Use of Vasoactive Medications by Day 14 :
 
event = "Y" if Vasoactive Medications = "Y" and date/time of daily collection is performed between Date/time of 1st IMP intake and Day 14 (date/time).
 
otherwise
 
event = "N" if last available day>=12 (allowed time window of 2 day for Day 14 visit)
 
otherwise event is missing if last available day<12
 
Day 14= Day1 (date/time 1st IMP intake) + 13

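### The Day 7 oxygenation index co-primary has no rule for ECMO, so an ECMO-supported OI is scored as observed and can look like improvement

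*SAP*

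**What the plan says.** **Definition.** SAP 11.1.1 gives OI as "derived as 100 x mean airway pressure x FIO2/PaO2". There is no term for extracorporeal oxygenation.

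**Scoring.** The same section takes the Day 7 value from the window 132 h to 155 h 59 min after first dose: "If there is one measurement of mean airway pressure and one measurement of FiO2/PaO2 falling in that specific study day", those two values are used. If either is missing, OI is not derived. Protocol 6.1.3 has the components collected daily until extubation, with no stop at ECMO.

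**Intercurrent events (SAP 4.4.1, estimand #1).** There are three:
- "Death before Day 7, or at Day 7 if OI is not present, as a terminal event which precludes the observation of the variable": composite, 90th percentile of observed values.
- "For patients that at day 7 are extubated and OI is not evaluable, extubation will be handled by the composite strategy": 10th percentile of observed values.
- "Treatment discontinuation, which may affect interpretation of the variable, will be handled by the treatment policy strategy".

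**ECMO elsewhere.**
- Protocol 4.2 excludes patients "Currently receiving ECMO or high frequency oscillatory ventilation", so any ECMO in the trial starts after entry.
- Protocol 3.3 says "prone positioning, and use of ECMO are left to the" investigator's discretion.
- SAP 3.5.2 and 7.2.1.5 analyse ECMO incidence at Day 14 as a secondary endpoint. SAP 11.1.1 derives it by date from a yes/no transition field in "Daily assessments through extubation".
- Protocol 6.5 also lists duration of ECMO, in days, among the data to record.

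**The concern.** OI is meant to describe how well the patient's lungs oxygenate at a given ventilator pressure. If ECMO raises PaO2, or lets FiO2 or mean airway pressure be reduced, OI falls and the patient scores as improved, although the improvement comes from the circuit. The SAP handles treatment discontinuation because it may affect interpretation of the variable. The same reason applies to ECMO, yet no strategy is stated for it.

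Three consequences follow from the rules as written:
- An intubated patient on ECMO keeps the observed value.
- That value enters the distribution behind the scores given to dead and extubated patients. If it is low, it can only lower those percentiles or leave them unchanged, which makes the death score milder and the extubation score more favourable.
- A patient extubated while on ECMO with no evaluable OI is scored as a success.

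If ECMO is commoner on placebo, a benefit of reparixin can be masked; if it is commoner on reparixin, reparixin can look better than it is. Because ECMO is discretionary, its use can also differ by site.

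**Working it through.** **1. Does any other rule catch the case?**

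| Place | Effect on a patient on ECMO with an OI at Day 7 |
|---|---|
| SAP 4.4.1, estimand #1 | ECMO not listed; observed OI kept |
| SAP 4.10, missing data | Applies only if OI is missing; no mention of ECMO |
| SAP 7.1.2.1, MAR sensitivity | Changes imputed values only |
| SAP 7.1.3.1 to 7.1.3.5 | No ECMO condition |
| SAP 7.1.3.6, still intubated at Day 7 | Keeps ECMO patients |
| Protocol 5.3.2, IMP discontinuation | ECMO not a criterion; discontinuation would in any case leave the observed value in use |
| SAP 11.1.1, Day 4 OI | Derived in the same way as Day 7 |

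None does. Parts of the SAP revision history and SAP 4.11 are blacked out, but no redaction is marked in the estimand or OI derivation text.

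**2. The plan's precision figure.** SAP 3.3 gives a one-sided 95% margin of at most 46.5% of the SD, with SD 11.5 and 60 evaluable patients. 0.465 x 11.5 = 5.35 points, as stated. The plain half-width is t(0.95, 58) x sqrt(2/30) = 0.432 SD. With 80% assurance on the width (my assumption) it is 0.463 SD, so 46.5% is reproduced. The point here does not depend on this; 5.35 serves only as a yardstick.

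**3. Can OI fall on ECMO?** Ventilator settings below are assumed; the documents give none.
- Airway pressure 18, FiO2 0.8, PaO2 70: 100 x 18 x 0.8/70 = 20.6. On ECMO, 12, 0.4 and 90: 100 x 12 x 0.4/90 = 5.3. Change -15.3.
- Milder: airway pressure 18 with PaO2/FiO2 100 gives 18.0; on ECMO, 12 with 150 gives 8.0. Change -10.0.
- Counter-example: 15 with 150 gives 10.0; on ECMO, 12 with 80 gives 15.0. Change +5.0, scored as worse.

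Improvement is possible, not certain.

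**4. Effect of scoring one such patient as a failure.** Assume Day 7 OI is lognormal with SD 11.5 (the SAP gives this SD when sizing the change in OI; its use at Day 7 is my assumption) and mean 10, 14 or 18. The 90th percentile (P90) is then 21.3, 27.2 or 32.1. With 66/2 = 33 per arm, the shift in an arm mean is (P90 - OI on ECMO)/33:

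| OI on ECMO | P90 21.3 | P90 32.1 |
|---|---|---|
| 5.3 | 0.48 | 0.81 |
| 8.0 | 0.40 | 0.73 |

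So 0.4 to 0.8 points per patient, or 7% to 15% of 5.35. A net imbalance of two patients gives 0.8 to 1.6 points. If rescoring moved a patient by only 5 points, the shift would be 5/33 = 0.15. These are shifts in raw means; the covariate-adjusted difference would move by a similar amount.

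**The case against.** The strongest reply is that the documents show an omission, not a bias. They give no ECMO rate and no OI on ECMO, and some ECMO patients would still score as worse. If a component is missing in the window, the patient goes to imputation instead. The trial is descriptive, ECMO incidence is compared by arm, and the ventilator-free-days co-primary counts intubated days, so an imbalance would be partly visible. Proning, neuromuscular blockers and inhaled vasodilators are also discretionary, may also affect OI, and are not handled either. A treatment-policy strategy for ECMO would be legitimate.

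Most of this stands as a limit on size and certainty. It does not close the gap: a separate incidence table does not correct the co-primary, and a treatment-policy choice has to be stated.

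Three stronger readings are tempting and not supported:
- That ECMO always makes OI look better. The counter-example above shows otherwise.
- That this plan already treats ECMO as failure. An entry exclusion and an incidence endpoint do not say so. The COVID-19 trial summarised in Protocol 2.5 counted need for ECMO within respiratory failure, but that is a different trial's endpoint.
- That every ECMO patient should simply be set to the 90th percentile. That would upgrade a patient whose observed OI is already higher.

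Two objections to any failure score also stand. A Day 7 death with an OI present keeps its observed value, so an ECMO survivor could score worse than that patient. And because the endpoint is a change, a baseline OI of 25 against a 90th percentile of 21.3 still gives -3.7. The existing death score shares this second weakness.

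**Conclusion.** The gap is real and follows from the text alone: neither estimand #1 nor the OI derivation at Day 7 or Day 4 says what happens on ECMO, and the default is to score the supported value as the patient's own oxygenation. Its consequence is confined to patients on ECMO in the window who have both measurements, or who are off the ventilator with no evaluable OI. Size is a range under assumption, about 0.4 to 0.8 points per patient on a 33-patient arm mean. It rests on an assumed OI on ECMO of 5 to 8 and an assumed lognormal Day 7 distribution. The net effect on the treatment difference depends on ECMO imbalance, which is unknown in size and sign. With few ECMO patients it would be small against 5.35 points. The effect on the percentiles was not quantified. This is a cheap improvement worth making, not a defect that invalidates the co-primary.

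**What to change.** Before unblinding, amend SAP 4.4.1, 7.1.1.1 and 11.1.1:
1. Add ECMO in the Day 7 window as an unfavourable composite event, scored at the worse of the observed OI and the 90th percentile, and let it override the extubation rule.
2. Compute the 10th and 90th percentiles without OI values recorded on ECMO.
3. Apply the same rule at Day 4.
4. Derive ECMO status by calendar date, as the SAP already does for death, from the daily transition field and the recorded ECMO duration. State the precision limit: the field records transition rather than current status, the daily form stops at extubation, duration is in days, and the OI window is defined in hours. Confirm that status can be derived before relying on it.

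If the sponsor prefers to keep observed values in the main analysis, state treatment policy for ECMO explicitly and pre-specify the ECMO-as-failure analysis as supplementary for this co-primary. If unblinding has occurred, report it as a labelled post-hoc analysis, which SAP 4.1 allows.

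Cost: SAP wording and a few lines of programming, with no new data collection provided step 4 confirms the status. Downside: a few observed values are replaced by a failure score.

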Day 3	1 st IMP intake Date/Time + 36h	1 st IMP intake Date/Time + 59h and 59 min	48h
Day 4	1 st IMP intake Date/Time + 60h	1 st IMP intake Date/Time + 83h and 59 min	72h
Day 5	1 st IMP intake Date/Time + 84h	1 st IMP intake Date/Time + 107h and 59 min	96h
Day 6	1 st IMP intake Date/Time + 108h	1 st IMP intake Date/Time + 131h and 59 min	120h
Day 7	1 st IMP intake Date/Time + 132h	1 st IMP intake Date/Time + 155h and 59 min	144h
Day 8	1 st IMP intake Date/Time + 156h	1 st IMP intake Date/Time + 179h and 59 min	168h
Day 9	1 st IMP intake Date/Time + 180h	1 st IMP intake Date/Time +203h and 59 min	192h
Day 10	1 st IMP intake Date/Time + 204h	1 st IMP intake Date/Time + 227h and 59 min	216h
Day 11	1 st IMP intake Date/Time + 228h	1 st IMP intake Date/Time + 251h and 59 min	240h
Day 12	1 st IMP intake Date/Time + 252h	1 st IMP intake Date/Time + 275h and 59 min	264h
Day 13	1 st IMP intake Date/Time + 276h	1 st IMP intake Date/Time + 299h and 59 min	288h

Standard/Forms/Template				
Title		Statistical Analysis Plan Template		
Code		Version	Effective Date	Page
PPD		01	29 Aug 2022	16 of 78

Day 14	1 st IMP intake Date/Time + 300h	1 st IMP intake Date/Time + 323h and 59 min	312h
--------	---	--	------

Differently from what it was reported in the study protocol, the window used for each day is +/- 12 hours to let each assessment to be unequivocally classified in a given day (not possible by using the time window +/- 8h).

With the exception of Day 1, which covers 12 hours (11 h and 58 minutes), all the other days cover 24 hours (23h and 59 min).

For each endpoint described in section 3.5.1 and 3.5.2, it will be specified whether the study Day will be defined on the basis of Date or Date/time. Section 11.1.1 provides further details with regards to variables derivations based on date or date/time.

Please refer to Table 1: Study Flow Chart for full details on the schedule of suggested assessments.

Notes:

- Study Days will be derived using the algorithms defined above.
- Analysis based on visits (Chest Imaging, labs, ECG ...) will use the assessments collected at that visit, regardless of the study days.

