3.5.1 Primary endpoint

- Change in oxygenation index (OI) from baseline to day 7 [study day: date/time]
OI defined as: % mean airway pressure x FIO₂/PaO₂ (A difference between groups in 7-days OI of 6.6 points was significantly associated with 28-days mortality (Go et al., 2016). Thus, such a difference in the change in 7-days OI, ranked as the most important endpoint, will be valued as a proxy of clinical success)
- Ventilator free days (VFD) at day 28 [study day: date/time]

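### Day 7 and Day 4 OI are built from a pressure and a blood gas chosen separately within a window of almost 24 h, with no pairing rule, unlike baseline OI

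*SAP*

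**What the plan says.** The first co-primary endpoint in SAP 3.5.1 is "Change in oxygenation index (OI) from baseline to day 7 [study day: date/time"]. According to SAP 11.1.1 (Table 3), "The implementation of the OI is based on 2 daily forms": mean airway pressure comes from the Mechanical Ventilation Parameters form and PaO2/FiO2 from the Lung Function form.

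**After baseline.** Each component is selected by the date/time study-day rule, and OI is computed "If there is one measurement of mean airway pressure and one measurement of FiO2/PaO2 falling in that specific study day". For Day 7, "Both mean airway pressure and FiO2/PaO2 should be collected in the window [First IMP Intake+132h, First IMP Intake+155h and 59min"]. Where a component has several readings, the rule is to "keep the assessment closer to the midpoint of the time interval", applied to each component on its own. If either component has no reading in that study day, OI is not derived. Day 4 OI is derived in a similar way. SAP 3.2.1 gives the length of a study day: apart from Day 1, "all the other days cover 24 hours (23h and 59 min").

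**At baseline.** The last pre-dose mean airway pressure of the day is the anchor. The FiO2/PaO2 used is the one "which is closest (and non missing) to the selected" pressure, within ±12 h and before the first dose. If there is none, a FiO2/PaO2 from the same calendar date is accepted.

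**The concern.** OI multiplies a ventilator setting by a measure of gas exchange, so it describes the patient only if both parts come from the same ventilator state. Over most of a day PEEP, FiO2 or body position can change, and the product may then match no state the patient was in. The SAP respects this at baseline, where the gas is tied to the pressure. After baseline the only tie is a shared window whose edges are fixed by the hour of the first dose. An edge can fall between the morning blood gas and the ventilator round, and the rule then joins one morning's pressure to the next morning's gas.

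The error could reach beyond the patients concerned. The 10th and 90th percentiles of observed Day 7 OI are imputed for patients who are extubated or have died, and retrieved dropouts' Day 7 values feed the imputation model.

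**Working it through.** **1. The plan's window.** Day 7 runs from 132 h to 155 h 59 min after the first dose: 155 h 59 min − 132 h = 1,439 min = 23 h 59 min. This reproduces the SAP's figure and is the largest possible gap between the components.

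**2. One reading per form per day is enough.** Take a first dose at 18:30, a gas at 05:00 and a ventilator form at 08:00 each day.
- Day 7 window: 06:30 on calendar day 7 to 06:29 on day 8.
- Pressure in the window: 08:00 on day 7 (133.5 h).
- Gas in the window: 05:00 on day 8 (154.5 h).
- Gap used: 154.5 − 133.5 = 21 h.
- Gas passed over: 05:00 on day 7 (130.5 h), which is 133.5 − 130.5 = 3 h away but is assigned to study Day 6.

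**3. Several readings in the window.** Take pressures at 132.00 h and 132.25 h, and gases at 132.00 h and 155.75 h. The midpoint is 144 h. The rule keeps the pressure at 132.25 h (11.75 h from the midpoint, against 12 h) and the gas at 155.75 h (11.75 h against 12 h). The gap is 23.5 h, although a gas 0.25 h from the chosen pressure is in the window.

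**4. What a mixed pair does to OI** (illustrative values, not from the documents; OI = 100 × pressure × FiO2 / PaO2).
- Day 7 state: 100 × 18 × 0.7 / 70 = 18.0.
- Next morning: 100 × 13 × 0.5 / 75 = 8.7.
- Day 7 pressure with next morning's gas: 100 × 18 × 0.5 / 75 = 12.0, which is 6.0 points below the Day 7 value.

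**5. How often.** The documents give no distribution of dose, gas or form times. I simulated the SAP rule under these assumptions: one gas and one ventilator form per day, the form centred at 08:00, the gas centred at the same hour or 3 h earlier, and a timing SD of 1-3 h on each. The table shows the share of derivable Day 7 pairs more than 12 h apart.

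| First dose | Gas and form at same hour | Gas 3 h earlier |
|---|---|---|
| 08:00-13:00 | 0-0.4% | 0-1.5% |
| Uniform over 24 h | 2-7% | 10-11% |
| 13:00-22:00 | 6-17% | about 31% |

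In the last two rows, at least about nine in ten of these pairs had a gas within 12 h of the chosen pressure that the rule did not use.

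**6. Effect on precision.** Suppose each such pair carries an independent 6-point error on top of the planning SD of 11.5 (SAP 3.3). The SD becomes √(11.5² + p × 6²).
- p = 0.02: 11.53, which moves the stated 5.35-point margin to 5.36.
- p = 0.11: 11.67, margin 5.43.
- p = 0.31: 11.98, margin 5.57.

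**The case against.** **The frequency is assumed.** This stands. The 31% figure needs both afternoon or evening first doses and a gas usually 3 h before the form; with late-morning first doses the problem almost disappears. A reader might infer that gaps near 24 h are common, but the documents do not show that. The protocol (6.1.3) lists gases and ventilator parameters in one daily set, and if sites complete both forms together the gaps are short.

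**The effect on the estimate is small and has no direction.** This also stands. The rule is the same in both blinded arms, and step 6 moves the margin by at most 0.22 points (5.57 − 5.35). A reader might infer a biased treatment difference, but nothing in the documents supports that. The trial is also descriptive, with no hypotheses specified.

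**Baseline is not clean either.** Correct. It anchors on the last pressure of the day rather than seeking the closest pair, and its same-date fallback can exceed 12 h. Two tempting readings therefore fail: that baseline is strictly capped at 12 h, and that only Day 7 carries this error. The difference that remains is the pairing rule.

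**The windows serve a purpose.** SAP 3.2.1 widened them to ±12 h so that each assessment belongs to exactly one day, and reaching over an edge gives that up. This is a real cost, but a limited one. Day 4 and Day 7 are the only post-baseline OI outcomes. Extended by 12 h each side, their ranges are 48 h to 95 h 59 min and 120 h to 167 h 59 min, so no gas can serve both. A nearest-pair rule confined to the window would keep the windows intact but would not repair the 18:30 example.

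**Conclusion.** The point holds as a defect of derivation, of minor to moderate weight. It is certain from the text that the post-baseline components are chosen independently, that no maximum gap is set, and that 23 h 59 min is the limit. How often a long gap arises is not known: about 0-1.5%, 2-11% or 6-31% of derivable pairs exceed 12 h, depending on the assumed hour of the first dose and the assumed gas and form times. The consequence is extra noise in Day 7 and Day 4 OI. It is probably small, but it is avoidable in a variable that SAP 3.5.1 ranks as the most important endpoint. The 6-point error and the margins in step 6 are illustrations only, because the documents give no within-day variability for either component. The SAP's conclusions are not shown to be at risk.

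**What to change.** In SAP 11.1.1, for Day 7 and Day 4:
1. Choose the mean airway pressure closest to the window midpoint.
2. Take the post-dose FiO2/PaO2 closest in time to that pressure, within ±12 h, even if it lies just over the window edge.
3. List the time gap for every derived OI, baseline included.
4. Report the present rule as a sensitivity analysis. If the data are already unblinded, leave the primary derivation alone and report the new pairing as a documented supplementary analysis.

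This turns the 21 h gap of step 2 into 3 h, and the 23.5 h gap of step 3 into 0.25 h. It costs a short SAP amendment and a small programming change; the SAP derivation already uses the dates and times of both components.

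The SAP should state the downside. A gas from the adjacent study day may define Day 7 OI. Some OI values will move between missing and derivable, which slightly alters the multiple-imputation set, the retrieved-dropout set and the 10th and 90th percentile values.
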